- Evaluate the complexity of cardiac surgery residents' learning curve for grafts quality assessment with HFUS as isolated technique.
- Evaluate the complexity of cardiac surgery residents' learning curve for grafts quality assessment with TTFM as isolated technique.

STUDY DESIGN AND DURATION

This is a prospective, observational, monocentric cohort study in which adult patients undergoing coronary artery bypass surgery will be enrolled.

The study will last four months: three months for patients enrollment and data collection and one month for statistical analysis and scientific paper writing.

The trial will start after obtaining favourable opinion from the local Ethics Committee and could be considered completed when all the eight cardiac surgery residents involved have reached primary endpoint.

INCLUSION CRITERIA

- Age ≥ 18 years old;
- Written informed consent;
- Indication to CABG surgery (both «on-pump» and «off-pump»);
- Stable angina, unstable angina or acute coronary syndrome without ST elevation (NSTEMI).

EXCLUSION CRITERIA

- Age ≥ 18 years old;
- Written informed consent;
- Indication to CABG surgery (both «on-pump» and «off-pump»);
- Stable angina, unstable angina or acute coronary syndrome without ST elevation (NSTEMI).

STUDY PROCEDURES

All patients with coronary artery disease and an indication for surgical revascularization (coronary artery bypass grafting) who meet the above-described inclusion and exclusion criteria will be enrolled by signing the informed consent the day before surgery.

Patient data (anamnestic data, surgery description, *intraoperative echographic and flowmetric measurements*) will be recorded in a dedicated database. All data recorded in the database are commonly acquired for all patients undergoing this type of surgery and no further examinations will be performed for patients included in the trial.

The study will involve cardiac surgery residents with different levels of training and an expert cardiac surgeon who acts as supervisor and benchmark. Each resident will sign a dedicated informed consent form in the presence of a doctor foreign to the study protocol (Cardiac Surgery ward cardiologist). The residents will be “blinded” about the trial objective and the adopted score system. They will undergo a specific training including a quick lesson and a practical workshop to familiarize with the equipment.

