During surgery, every graft will be evaluated through transit time flowmetry (TTFM) and intraoperative ultrasound control (HFUS).

In details, the ultrasound control is carried out through a dedicated sterile ultrasound probe connected to a machine (MiraQ - MEDISTIM) as soon as each anastomosis is completed. The result of the evaluation is recorded together with surgery data. This evaluation is intended to confirm the correct realization of the anastomosis and provides a proof of its patency.

Once each graft is completed, the resident will be given 60 seconds to acquire two HFUS recordings (short and long axis). After that, the supervisor will perform his personal recording which will stand as benchmark. The following items will be evaluated:

- A) Long axis recording acquired within 60 seconds [YES → 1] [NO → 0]
- B) Long axis recording judged as suitable by the supervisor [YES → 1] [NO → 0]
- C) Short axis recording acquired within 60 seconds [YES → 1] [NO → 0]
- D) Short axis recording judged as suitable by the supervisor [YES → 1] [NO → 0]

E) Correct interpretation of the anastomosis as adequate or inadequate [YES → no penalty] [NO → total score becomes 0 and the resident isn't allowed to perform TTFM]

Each resident will be given a HFUS-related score from a minimum of 0 to a maximum of 4. Whenever one of the recordings will be judged as non-suitable by the supervisor and consequently useless for a correct interpretation of the anastomosis (score 0 for items A and/or C), item E won't be evaluated and the HFUS will be given a total score of 0.

Next step will be the TFM evaluation, which is carried out through a specific sterile device connected to the same machine (MiraQ - MEDISTIM) once the patient has been weaned from the cardiopulmonary bypass and before protamine administration. This recording is performed under EKG and pressure-controlled conditions. Although there is no general agreement on the optimal mean arterial pressure at which the measurement has to be recorded, we will adopt the standard used in the REQUEST study protocol (16), that is an average pressure of 80 mmHg.

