The resident will acquire the TTFM recording after each graft is completed. To make the comparison as accurate as possible, the resident will perform TTFM evaluation on one graft at a time and successively the supervisor will do the same for each graft (making sure that delta between the pressure during the two recordings is lower than 10 percent and that no drug has been administered). The following items will be evaluated:

F) Time necessary to acquire the measures [$< 30 \text{ sec} \rightarrow 1$] [$> 30 \text{ sec}, < 60 \rightarrow 0.5$] [$> 60 \text{ sec} \rightarrow 0$]

G) Need for multiple measurements before the final one: [$> 2 \rightarrow 0$] [$1 \rightarrow 0.5$] [$0 \rightarrow 1$]

H) Need to change probe dimensions: [NO $\rightarrow 0$] [YES $\rightarrow 1$]

I) ACI [delta between resident and supervisor measurements $< 10\% \rightarrow 1$] [$> 10\%, < 20\% \rightarrow 0.5$] [$> 20\% \rightarrow 0$]

L) Mean Flow [delta between resident and supervisor measurements $< 10\% \rightarrow 1$] [$> 10\%, < 20\% \rightarrow 0.5$] [$> 20\% \rightarrow 0$]

M) Pulsatility Index [delta between resident and supervisor measurements $< 10\% \rightarrow 1$] [$> 10\%, < 20\% \rightarrow 0.5$] [$> 20\% \rightarrow 0$]

N) Backward Flow [delta between resident and supervisor measurements $< 10\% \rightarrow 1$] [$> 10\%, < 20\% \rightarrow 0.5$] [$> 20\% \rightarrow 0$]

O) Diastolic Filling [delta between resident and supervisor measurements $< 10\% \rightarrow 1$] [$> 10\%, < 20\% \rightarrow 0.5$] [$> 20\% \rightarrow 0$]

P) Correct interpretation of the graft quality as working [YES \rightarrow no penalty] [NO \rightarrow total score becomes 0]

Each resident will be given a TTFM-related score from a minimum of 0 to a maximum of 8.

The final score for each graft will be the sum of the two scores (HFUS and TTFM), from a minimum of 0 to a maximum of 12.

The same procedure will be repeated for each graft performed during the surgery.

Each resident will continue until reaching a ratio between total score and number of evaluated anastomoses of 11.

END-POINTS

Primary end-point

Number of anastomoses needed to reach a ratio (total score/n. of anastomoses) ≥ 11

Secondary end-points

- Number of anastomoses needed to reach a ratio (HFUS score/n. of anastomoses) = 4
- Number of anastomoses needed to reach a ratio (TTFM score/n. of anastomoses) ≥ 7

STATISTICAL ANALYSIS AND SAMPLE SIZE CALCULATION

Sample size calculation

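### Item E lets an ultrasound misreading decide whether flowmetry is scored, so the secondary end-point does not measure flowmetry in isolation

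*Combined protocol and SAP*

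**What the plan says.** Study Procedures scores each graft in two stages. HFUS comes first. Items A to D give one point each for timely and suitable long-axis and short-axis recordings: "Each resident will be given a HFUS-related score from a minimum of 0 to a maximum of 4". Item E then asks whether the resident judged the anastomosis correctly. If not, the rule is "NO → total score becomes 0 and the resident isn't allowed to perform TTFM".

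A separate branch covers recordings that the supervisor rejects: "item E won't be evaluated and the HFUS will be given a total score of 0". That branch does not mention TTFM, and the text goes on: "Next step will be the TFM evaluation". TTFM is scored on items F to O, and item P can cancel the score: "Each resident will be given a TTFM-related score from a minimum of 0 to a maximum of 8". The graft total is the sum of the two parts, at most 12.

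One of the two secondary objectives under Study Objectives is: "Evaluate the complexity of cardiac surgery residents' learning curve for grafts quality assessment with TTFM as isolated technique". The matching entry under End-points is: "Number of anastomoses needed to reach a ratio (TTFM score/n. of anastomoses) ≥ 7". The primary end-point uses the total score in the same way with a threshold of 11, and that ratio is also each resident's stopping rule.

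Neither End-points nor Statistical Analysis says whether a graft barred under item E counts as a TTFM zero, is missing, or leaves the denominator.

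**The concern.** A learning curve for TTFM alone should not move when only a resident's HFUS skill changes. Under item E it does, because a wrong HFUS reading removes the TTFM measurement on the same graft. There are two ways to handle that graft:

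- **Count it as 0.** An HFUS error is then recorded as a TTFM failure.
- **Leave it out.** The TTFM curve then rests only on grafts that were not misread on HFUS, and the resident loses a TTFM attempt.

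Two analysts could report different end-point values from the same data, and neither value would answer the stated objective. Residents with equal TTFM skill could also be given different TTFM curves.

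There is a related question for the primary score. The bar is attached to misread images but not, as written, to unsuitable ones, so the two kinds of HFUS failure lead to very different graft totals.

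**Working it through.** The plan gives no figure for the effect of the bar. The inputs are the score ranges and thresholds in Study Procedures and End-points.

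**1. The plan's score ranges.** HFUS items A to D: 4 × 1 = 4. TTFM items F, G, H, I, L, M, N and O: 8 × 1 = 8. Total: 4 + 8 = 12. All three agree with the plan. As printed, item H gives its point only when a probe change was needed. Without one, the TTFM maximum is 7 and the graft maximum is 11.

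**2. TTFM ratio, barred graft counted as 0.** Let the first k grafts be barred and every later TTFM score be s. The threshold is met when s(n − k)/n ≥ 7, that is n ≥ sk/(s − 7).

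- s = 8: n ≥ 8k, so 8, 16 and 24 anastomoses for k = 1, 2 and 3. Without the bar, n = 1.
- s = 7.5: n ≥ 15k, so 15 for k = 1.
- s = 7 (no item H point): 7(n − 1)/n stays below 7, so the threshold is never met.

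The position of the error matters. A resident who scores 7 or more on a first graft that is not barred has already met the criterion at anastomosis 1.

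**3. Long-run limit on the same reading.** With misreading rate e, the ratio tends to s(1 − e), which stays at or above 7 only if e ≤ 1 − 7/s. This is 12.5% for s = 8 and 6.7% for s = 7.5.

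**4. TTFM ratio, barred graft left out.** The ratio is s(n − k)/(n − k) = s. One misreading at the first graft costs only the skipped graft, so the criterion is met at the second anastomosis.

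**5. Illustration with assumed inputs.** The mean TTFM score rises from 6 towards 7.75, with SD 0.5, half-point scores capped at 8, and follow-up to 60 grafts. The median number of anastomoses to reach a TTFM ratio of 7 is:

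| Misreading rate | Counted as 0 | Left out |
|---|---|---|
| 0% | 12 | 12 |
| 5% | 15 | 12 |
| 10% | 40 | 12 |
| 20% | more than 60 | 11 |

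Misreadings were drawn independently of the TTFM score, and skill rose with every graft, barred or not. The last column therefore shows no effect of selection or lost practice, because neither was modelled.

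**6. The two HFUS failures in the primary score.** One such graft comes first, and every later graft scores 12 (including the item H point).

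- Suitable images, misread: graft total 0. Then 12(n − 1)/n ≥ 11 gives n = 12.
- Unsuitable image, TTFM of 8 still taken: graft total 0 + 8 = 8. Then (12n − 4)/n ≥ 11 gives n = 4.

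On the HFUS score alone, both cases give 0.

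**The case against.** **A reader might infer that TTFM will look harder to learn than it is.** That direction needs the count-as-zero reading. The end-point divides by the number of anastomoses, but the stopping rule refers to those evaluated, so exclusion is an available reading, and under it the numerical penalty largely disappears. Nor does the Background supply the direction. The specific HFUS difficulty it describes is mainly one of acquiring the image, whereas the bar is triggered only by misinterpretation. It places the risk of diagnostic errors with TTFM. This objection stands.

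**A reader might infer that the scale wrongly rewards failed imaging.** The documents do not establish that either. Item P likewise cancels a score for a wrong interpretation, so item E may be a deliberate critical-error penalty, and ranking a wrong verdict below no verdict is defensible in a competence score. The Background also asks for TTFM to be interpreted together with HFUS, which fits gating in a combined score. The comparison further rests on silence in a sentence that cites items A and/or C, although suitability is scored in B and D. This stands too, and the comparison remains a question for the investigators.

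**The worked figures are best cases.** A TTFM score of 8 needs the item H point on every graft, and no item E error rate is given. Both are correct.

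**Every graft is still assessed.** The supervisor also measures each graft, so the general statement that all grafts are evaluated by both techniques does not contradict the bar.

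None of this removes the conflict for the secondary end-point. Even if the total score in item E means only the HFUS total, the bar still withholds the TTFM points.

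**Conclusion.** The conflict holds and should be fixed. Item E makes the TTFM measurement conditional on the HFUS interpretation of the same graft, while the objective and its end-point are meant to describe TTFM alone. No handling of a barred graft restores that isolation.

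On the printed denominator, one misreading at the first graft moves a resident with maximal TTFM scores from 1 to 8 anastomoses. That figure assumes the barred graft counts as 0 and every later TTFM score is 8, including the item H point. With exclusion the shift is small, and the remaining problem is selective observation and lost practice, which the documents give no means to quantify. Because the item E error rate is not stated, the actual size is unknown.

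For the primary score, up to 8 of 12 against 0 of 12 is what the two branches give as written. It is a point to reconcile and confirm, not a demonstrated error.

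**What to change.** Decouple the TTFM score from item E. An item E error would set only the HFUS score to 0, and the resident would acquire and be scored on TTFM on every graft. The TTFM end-point would then use all of that resident's grafts. This is one sentence of protocol wording, and the cost in theatre is one more short resident reading on misread grafts. If the investigators want a graft total of 0 after a misreading in the primary score, they can keep that and still score TTFM separately for the secondary end-point.

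Whether a resident proceeds to TTFM is a conduct decision for the investigators. If they keep the bar, they should compute the TTFM ratio only over grafts on which the resident performed TTFM, state this under End-points, report the number of barred grafts per resident, and stop describing the end-point as isolated. The cost is a curve conditional on HFUS interpretation.

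In either case, they should reconcile the misread-image and unsuitable-image branches. They should correct the item letters in the unsuitable-image sentence, state whether TTFM follows in that branch, and confirm whether the resulting ranking is intended in the primary score.

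### The HFUS zero-score rule names the timing items (A, C) where its words describe the suitability items (B, D), so up to 6 of 16 scoring patterns have two possible scores in the primary endpoint

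*Combined protocol and SAP*

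**What the plan says.** All of this is in the combined protocol and SAP.

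- **Timing items** (STUDY PROCEDURES): "A) Long axis recording acquired within 60 seconds" and "C) Short axis recording acquired within 60 seconds", each worth 1 or 0.
- **Suitability items** (same list): "B) Long axis recording judged as suitable by the supervisor" and "D) Short axis recording judged as suitable by the supervisor", each worth 1 or 0.
- **Item E**, the interpretation of the anastomosis, carries no points. A wrong answer means "total score becomes 0 and the resident isn't allowed to perform TTFM".
- **Zero rule** (after the item list): it applies when a recording is "judged as non-suitable by the supervisor and consequently useless for a correct interpretation of the anastomosis (score 0 for items A and/or C"). The consequence is that "item E won't be evaluated and the HFUS will be given a total score of 0".
- **Time window**: the resident "will be given 60 seconds to acquire two HFUS recordings (short and long axis). After that, the supervisor will perform his personal recording".

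The HFUS score (0 to 4) is added to the TTFM score (0 to 8) to give a graft total of 0 to 12. Under END-POINTS, the primary endpoint is the number of anastomoses until the cumulative total divided by the number of anastomoses is at least 11. STUDY PROCEDURES makes the same ratio each resident's stopping point.

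**The concern.** The sentence gives one trigger in words and another in letters. The words, and the reason attached to them (an image that cannot be interpreted), describe a 0 on B or D. The parenthesis identifies the event as a 0 on A or C, which means late acquisition. This is probably a slip of item letters, but a scoring sheet or database formula would be built from the letters.

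Two things are at stake. First, the same graft can differ by 2 or 3 points when the target leaves only one point of slack per graft. Secondly, in the disputed patterns the readings also differ on whether item E is judged, and a wrong item E removes the resident's TTFM recording. Which data exist can therefore depend on the reading used in theatre. The same ratio decides when a resident stops, so someone who stopped under one reading has no later grafts to rescore under the other.

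**Working it through.** **Inputs.** Items A–D, each 0 or 1, and the ranges HFUS 0–4, TTFM 0–8 and total 0–12 come from STUDY PROCEDURES. The target of 11 comes from END-POINTS. Item E is taken as correct wherever it is judged.

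**The plan's own range.** A+B+C+D runs from 0 to 4, as stated.

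**The two readings.**

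- Words: HFUS = 0 if B = 0 or D = 0; otherwise A+B+C+D.
- Letters: HFUS = 0 if A = 0 or C = 0; otherwise A+B+C+D.

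Of the 2⁴ = 16 patterns, these differ:

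| A B C D | Meaning | Words | Letters |
|---|---|---|---|
| 1 0 1 1 | both timely, long axis unsuitable | 0 | 3 |
| 1 1 1 0 | both timely, short axis unsuitable | 0 | 3 |
| 1 0 1 0 | both timely, both unsuitable | 0 | 2 |
| 0 1 1 1 | both suitable, long axis late | 3 | 0 |
| 1 1 0 1 | both suitable, short axis late | 3 | 0 |
| 0 1 0 1 | both suitable, both late | 2 | 0 |

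Of the other ten, 1111 scores 4 under both readings and nine score 0 under both. So 6 of 16 are in dispute.

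**If a late recording cannot be suitable**, each view has three states (late, timely but unsuitable, timely and suitable). That gives 3 × 3 = 9 patterns, and only the first three rows remain: 3 of 9. The words then allow only scores of 0 or 4; the letters allow 0, 2, 3 and 4.

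**Item E.** Whether it is judged differs in exactly the disputed patterns. For a timely but unsuitable view, the words skip E. The letters judge it, and a wrong answer bars TTFM.

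**Effect on the primary endpoint (illustration only).** Further assumptions: TTFM is done on every graft and all other items are at maximum. Let p be the share of grafts earning the item H point, which as printed requires a probe change. Let k of n grafts have one timely but unsuitable view. Such a graft loses 4 HFUS points by the words and 1 by the letters, so:

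- Words: ratio = 11 + p − 4k/n, which is at least 11 only if k/n ≤ p/4.
- Letters: ratio = 11 + p − k/n, which is at least 11 only if k/n ≤ p.

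| p | Largest k/n, words | Largest k/n, letters |
|---|---|---|
| 1 | 25% | 100% |
| 0.5 | 12.5% | 50% |
| 0 | 0 | 0 |

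At p = 1 and n = 12, this allows 3 such grafts by the words and 12 by the letters.

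**Single-graft example, p = 1.** The first graft totals x and all later grafts total 12. Then (x + 12(n − 1))/n ≥ 11 gives n ≥ 12 − x.

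- One unsuitable view: by the words x = 8 + 0 = 8 and n = 4 (check: (8 + 36)/4 = 11). By the letters x = 8 + 3 = 11 and n = 1.
- Both views unsuitable: by the words n = 4. By the letters x = 8 + 2 = 10 and n = 2.

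**Where it makes no difference.** At p = 0 no graft exceeds 11. One such graft before the target is reached then puts the target out of reach under both readings. The secondary endpoint of an HFUS ratio equal to 4 is also unaffected, because 0, 2 and 3 all fall short of 4.

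**The case against.** The strongest reply is that nobody would misapply the rule. The main clause names who judges, what is judged and why item E is skipped, and the parenthesis is only a mislabel. The supervisor who judges suitability can be expected to follow the words. As a guide to intent this is persuasive, and it is why the correction follows the words. It does not make the printed rule usable, because its only reference to scored items is to the wrong ones.

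Secondly, three of the six patterns need a late recording to be rated suitable, and the supervisor's own recording follows the 60 seconds. This makes 3 of 9 the more natural count, but the text does not exclude the other three patterns.

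Thirdly, the endpoint figures rest on stacked assumptions, and the largest contrasts need p = 1. This stands: they show possible sensitivity, not expected impact.

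Finally, the loss of data is conditional. If the words are applied and late recordings cannot be suitable, A–D alone fix the HFUS score. TTFM is lost only if the site applied the letters, the views were timely with at least one unsuitable, and item E was wrong. That limits how often it can happen, but where it does, storing A–D separately will not recover the recording.

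**Conclusion.** The concern holds. The zero rule contradicts the item list it refers to, and the document offers no resolution. With item E correct where judged, 6 of 16 A–D patterns have two possible HFUS scores, 2 or 3 points apart, or 3 of 9 if late recordings cannot be suitable. These counts need no assumption about frequency.

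The consequence for the primary endpoint cannot be sized from the document. Under the illustrative assumptions it ranges from none (p = 0) to a fourfold difference in the tolerated share of grafts with one timely but unsuitable view (any p above 0). The rule should be corrected because it feeds the primary endpoint and the stopping point, although the likely cause is only a mislabelled cross-reference.

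**What to change.** Before scoring starts:

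1. In the zero rule's parenthesis, replace items A and C with items B and D, so that the letters match the rule's own words and reason.
2. Have the sponsor confirm whether a suitable recording obtained after 60 seconds loses only its timing point or also triggers the zero. If it also triggers the zero, or if late recordings can never be suitable, the HFUS score can only be 0 or 4, and the protocol should say so.

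While editing the sentence, it would help to state whether the resident goes on to TTFM when item E is skipped, which the text implies but does not say. If scoring has already begun, record which reading was applied to each graft.

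The cost is one wording correction and one confirmation, with no new data, procedures or staff. The downside to disclose is that timely but unsuitable grafts will score 0 rather than the 2 or 3 the printed letters allow, so residents may take longer to reach the target.

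### On the main clause of the zeroing rule the 0 to 4 HFUS score can only be 0 or 4, and no per-axis analysis is planned that would show partial progress

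*Combined protocol and SAP*

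**What the plan says.** The Secondary objectives include the "learning curve for grafts quality assessment with HFUS as isolated technique". In Study Procedures, "the resident will be given 60 seconds to acquire two HFUS recordings (short and long axis"), after which the supervisor makes the benchmark recording. Each axis carries two items, one for time and one for suitability. For the long axis these are "A) Long axis recording acquired within 60 seconds [YES → 1] [NO → 0"] and "B) Long axis recording judged as suitable by the supervisor [YES → 1] [NO → 0"]; items C and D do the same for the short axis. Item E (interpretation) carries no points, but an error sets the score to zero.

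The section states the scale: "Each resident will be given a HFUS-related score from a minimum of 0 to a maximum of 4". The next sentence says that when either recording is found unsuitable, and so of no use for interpreting the anastomosis, item E is skipped and "the HFUS will be given a total score of 0". A parenthesis in that sentence identifies the trigger as a zero on item A and/or item C, which are the time items; suitability is scored in B and D.

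The End-points section defines the HFUS endpoint as the number of anastomoses until the cumulative HFUS score per anastomosis equals 4, and the primary endpoint as the number until the cumulative total score per anastomosis is at least 11. The Statistical analysis section plans no learning-curve model and no analysis by item or by axis.

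**The concern.** A study of a learning curve needs a measure that moves as skill is gained. Four items are scored per graft, but the zeroing rule appears to remove every intermediate value. A resident who has mastered the long axis and not yet the short axis is then scored like one who recorded nothing. The HFUS score becomes a pass/fail string, although the Background describes mastery as gradual and HFUS as the harder of the two techniques. The same zero carries into the primary endpoint, where the margin between the maximum of 12 and the threshold of 11 is only one point per graft.

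**Working it through.** **Inputs.** From Study Procedures: items A to D, each 0 or 1; the 60-second limit; the zeroing sentence and its parenthesis; maximum TTFM score 8 and maximum total 12. From End-points: an HFUS ratio equal to 4 and a total ratio of at least 11.

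**1. The stated range.** If a view not acquired in 60 seconds cannot be suitable, then B ≤ A and D ≤ C, which leaves 3 × 3 = 9 patterns. Adding A + B + C + D with no zeroing for unsuitability gives 0, 1, 2, 3 and 4, so the stated range is reproduced.

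**2. The range after zeroing, by reading (item E correct).**
- Main clause (B = 0 or D = 0 gives 0), 60 seconds final: a non-zero score needs B = D = 1, which forces A = C = 1. Possible scores: 0 and 4.
- Main clause and parenthesis together (any of A to D at zero gives 0): 0 and 4, whether or not late recordings count.
- Main clause only, with a late but suitable recording counted: B = D = 1 with A and C free. Possible scores: 0, 2, 3 and 4. One suitable view still scores 0.
- Parenthesis only (A = 0 or C = 0 gives 0): A = C = 1 with B and D free. Possible scores: 0, 2, 3 and 4. An unsuitable view would then not zero the score, which contradicts the main clause.

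No reading yields the full 0 to 4 scale.

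**3. How much one-view progress is hidden (illustration).** Assume each view succeeds independently with probability p, a failed view earns nothing, and interpretation is correct. The share of grafts with exactly one good view is 2p(1 − p): 50% at p = 0.5, 42% at 0.7, 18% at 0.9. On the main clause all of these score 0. Mean HFUS is 4p² zeroed against 4p additive: 1.00 against 2.00, 1.96 against 2.80, and 3.24 against 3.60.

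**4. Effect on the primary ratio (main clause).** A graft with one unsuitable view totals at most 0 + 8 = 8. With m later grafts at 12, (8 + 12m)/(1 + m) ≥ 11 gives m ≥ 3. Under additive scoring the same graft would total 3 + 8 = 11 if the poor view was acquired, or 2 + 8 = 10 if it was not.

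If a fraction q of a resident's grafts so far is zeroed this way and everything else is perfect, the ratio is 12 − 4q, and 12 − 4q ≥ 11 requires q ≤ 25%. If mean TTFM is 7.7 (an assumption), 11.7 − 4q ≥ 11 requires q ≤ 0.7/4 = 17.5%.

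**5. The HFUS endpoint.** The maximum per graft is 4, so a cumulative mean of 4 requires every graft so far to score 4. It is met at graft 1 or never. With one imperfect first graft and 19 perfect ones, the ratio after 20 is 76/20 = 3.80 if the first scored 0, 78/20 = 3.90 if it scored 2, and 79/20 = 3.95 if it scored 3. Dropping the zeroing does not change this.

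**The case against.** The strict rule is deliberate and reasoned: without a usable recording the anastomosis cannot be interpreted, so item E cannot be assessed. Items E and P also zero a score, so all-or-nothing competence scoring runs through the plan. This stands, and it supports keeping the strict score for the primary endpoint. It does not supply a curve for the HFUS objective.

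The result also depends on the reading. If the parenthesis governs, a graft with both views acquired and one unsuitable scores 3 and can total 11, with no deficit. This stands too. A reader might infer that the plan makes HFUS pass/fail without qualification; the documents support that only on the main clause with the time limit final, or on both parts of the sentence together.

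Three further inferences go too far:
- That the item data are thrown away. The items are to be evaluated and intraoperative measurements stored, and nothing says item scores are deleted. What is missing is a planned analysis.
- That removing the zeroing would repair the HFUS endpoint. Step 5 shows that it would not.
- That the rule adds a definite number of anastomoses to the primary count. The documents give no success rate per view and no speed of learning, so no such figure can be defended.

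**Conclusion.** The point holds conditionally. On the main clause with a final 60-second limit, HFUS takes only the values 0 and 4, and progress on one view does not appear in the score. The running ratio still moves, but only as a pass rate. The three-graft recovery and the 25% ceiling are exact on that reading with TTFM at its maximum; the 17.5% ceiling rests on the assumed TTFM mean. The shares in step 3 rest on independence and an assumed p.

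Zeroing is one of two reasons why the HFUS objective has no usable curve; the other is an endpoint set at the maximum of a cumulative mean. This is an inexpensive improvement to the secondary analysis, not a case against strict scoring of competence.

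**What to change.** - Reconcile the zeroing sentence with its parenthesis: state which items trigger the zero, and whether a recording completed after 60 seconds can count.
- Keep items A to D in the database as scored, before any zeroing, next to the zeroed score.
- For the HFUS secondary objective, report by graft number the success per axis (long and short separately) and the raw additive 0 to 4 score, instead of relying only on the count to a ratio of 4.
- Keep the strict zeroed score for the primary endpoint. An additive version of the primary is not worth adding: a graft with one acquired but unsuitable view and perfect TTFM would already total 11, so the threshold could be met at the first graft.

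The cost is wording in the scoring, database and analysis sections; no new measurement or patient burden is involved. The drawback is that the additive curve gives partial credit to a graft with an unusable view, so it should be presented as a description of skill acquisition and not as evidence of competence.
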